Stimulating needle electrodes are placed at the wrist and ankle for the evaluation of the median and tibial nerves, respectively and SSEPs are recorded using electrodes over the scalp. A warning signal is generally issued when there is a 50% decrease in amplitude or 10% increase in latency compared with baseline values.⁽⁶⁾

SSEPs signal changes, however, are not always related to a postoperative neurological deficit. The specificity of SSEP during IONM was reported as 27%, whereas the sensitivity was 99%. ⁽⁷⁾ The use of SSEPs is advantageous because it does not provoke unwanted movement of the patient during surgery; and it is easily quantifiable. ⁽⁸⁾

Transcranial Motor Evoked Potential (tcMEP) is recognized as the most sensitive technique compared with SSEP.⁽⁸⁾ It monitors the corticospinal pathway and aids in early detection of neurological dysfunction. ⁽⁹⁻¹¹⁾ Trans cranial electrical stimulation via electrodes placed on the scalp over the motor cortex area is usually employed for the generation of MEPs and hence stimulation of the corticospinal tract. A short train of 5-7 electrical pulse stimuli with high frequency are usually used because it can generate action potential more easily through the summation of the excitatory postsynaptic potentials. MEPs can be recorded over muscle (Tc-mMEP) or over the spinal cord (D and I waves). Of these, Tc-mMEP seems to be the most widely adopted approach because of the relative simplicity of generating and recording MEPs. ⁽⁸⁾

MEP amplitude decrements >50% of baseline values were considered indicative of significant change, provided that the levels of neuromuscular blockade and general anesthesia were unchanged. ⁽¹²⁾ MEP can also detect hemodynamic changes like hypotension changes, positioning change and spinal cord or roots compression. Only few studies report the alarm criteria of MEP or SSEP for decompression surgeries. ⁽¹³⁾

Propofol causes less suppression of MEP than inhalational agents. Consequently, propofol and opioid total intravenous anesthesia (TIVA) is widely recommended in intraoperative monitoring. ⁽¹³⁾ Deepening anesthesia and administering boluses reduces or obliterates muscle MEPs, whereas lightening anesthesia increases them. Stable anesthesia is desirable, but adjustments may be medically indicated and it is necessary to track them. Short acting neuromuscular

blockade is often used to aid intubation of the patient during induction of anesthesia.⁽¹³⁾

In addition, Free-running Electromyography (EMG) has been used as a real-time monitoring modality to complement SSEP and tcMEP.⁽⁸⁾ It detects mechanical and/or metabolic irritation of the nerve. It can be recorded in the innervated muscles without electrical stimulation of the nerve.⁽⁸⁾

Two types of discharge, each with different clinical significance, can be observed using free-running EMG monitoring: tonic discharge and phasic discharge. Tonic discharge consists of repetitive and steady episodes of activity from grouped motor units that can last from several seconds to minutes; it can be observed in nerve ischemia due to traction, heat spread from electro cautery, or irrigation with saline. In contrast, phasic (burst) discharge is a short and relatively synchronous burst of motor unit potentials, which is mostly associated with blunt mechanical trauma.⁽⁸⁾

The old version of intraoperative assessment, wake-up test, might be occasionally carried out when traditional neurophysiologic monitoring is not available. In this procedure, the patient is awakened on the surgery table, with the wound still open and the patient intubated. Narcotics are used to relieve pain. When sufficiently awake, the patient is instructed loudly to move each extremity to detect if there is injury of spinal cord. Problems can occur if the patient is too confused to cooperate, or if the patient becomes agitated, he might move on the table, extubate himself, knock out intravenous lines, or cause other difficulties, Awakening of patient also may increase blood pressure of patient and cause excessive bleeding.⁽¹⁴⁾

Universally IONM is mandatory now in correction surgery for spinal deformities with high sensitivity and specify in detecting deficit.⁽¹⁵⁾ IONM of MEP in deformity surgeries can be focused during the time of maximal

manipulation of neural elements, such as during screws insertion and correction. In contrast, during decompression for cervical myelopathy, the risk to the spinal cord and nerve roots exists throughout the entire decompression procedure and not during a defined short period. ⁽⁹⁾ Moreover, the risk may be present even before the procedure during positioning of the patient's neck during intubation. Despite that, the indications for monitoring in cervical decompression surgeries are still controversial. ^(3,16) Some advocate its use ⁽⁹⁻¹¹⁾ while others argue against. ^(3,16)

To use only a single modality is not enough for a successful and efficient neuromonitoring in neurosurgery. It has been shown that multimodal monitoring has a high specificity and sensitivity in detecting postoperative neurological injury.⁽¹⁷⁾ Therefore, it is suggested to use appropriate multimodal intraoperative neuromonitoring techniques for various surgeries to avoid any neurological damage.

AIM OF THE WORK

1. To assess the usefulness of applying appropriate different neuromonitoring modalities in various neurosurgical operations with high risks of neural injury
2. To enhance our clinical experience and technical skills on various neuromonitoring techniques.

SUBJECTS

Twenty five patients with different brain or spine lesions will be admitted to Neurosurgery Department in Alexandria Main university hospital and are scheduled to undergo surgery under Intraoperative neurophysiological monitoring. Multimodal neuromonitoring techniques such as Somatosensory-evoked potentials (SEP), transcranial electrical stimulation–motor-evoked potentials (TES-MEP) , Free-running, Triggered Electromyography (EMG) and electromyographic monitoring of different cranial nerves will be used during the operation.

Inclusion criteria:

All patients will meet the following inclusion criteria:

- 1) Adults > 18 years
- 2) Brain or spine lesion close to eloquent area indicated for neuromonitoring.
- 3) Magnetic Resonance Image (MRI) for the site of lesion reflecting neural injury risks.

Exclusion criteria:

- 1) presence of vascular clips, intracranial electrodes, pacemakers, other implanted bio-mechanical equipment, cortical lesions, skull defects, increased intracranial pressure, and history of epilepsy

METHODS

Preoperative assessment:

All patients will be subjected to the following:

- 1- Clinical Examination including history taking, symptoms & signs.
- 2- Complete neurological examination.
- 4- All patients will be consented for Intraoperative neurophysiological monitoring (IONM) as a part of the surgical informed consent process.

Intraoperative Procedures:

Anesthesia

Total intravenous anesthesia (TIVA protocol) will be used: Induction of anesthesia will be performed with fentanyl 1 µg/kg and propofol 2 mg/kg intravenous, followed by a short acting muscle relaxant such as succinyl choline to facilitate tracheal intubation. Anesthesia will be maintained with 50% oxygen in air and propofol infusion. The infusion starts at 12 mg/kg/h and then decreased gradually to 6–10 mg/kg/h. The infusion rate is then adjusted according to hemodynamic responses to maintain a mean arterial pressure (MAP) between 60 and 70 mmHg.⁽¹⁹⁾

Monitoring Technique

Multimodal IONM (MIONM) for different pathologies will include SSEP and TES-MEP for spinal and cranial operations and free-run, triggered EMG would be used for brainstem operations in which cranial nerves were at risk.

Monitoring Technique ISIS IOM Neuromonitoring System (Inomed, Emmendingen, Germany) will be used for MIONM procedure. Monitoring will be throughout the surgery.

Monitoring will be divided into 3 stages: pre baseline, baseline, and monitoring.

Pre baseline includes period from patient's arrival to the operation room to baseline recordings. It will take about 40 minutes long and allow us to check the system and signal. This time covers equilibration of the anesthetics and elimination of muscle relaxants used for induction, which cause variability in recorded signals. ⁽²⁰⁾

Baseline is the period just before the high-risk manipulation of surgeon. Baseline data will be recorded and used as reference in monitoring period during the rest of the surgery. ⁽²⁰⁾

Anesthesia will be maintained by total intravenous anesthesia. Muscle relaxants will be used only for intubation and then will not be administered again except in cases that will require monitoring, which does not include MEP and EMG. ⁽²¹⁾

Transcranial Motor evoked potentials monitoring:

TcMEPs will be performed using transcranial stimulator over cortical motor area. The electrodes will be placed over the motor cortical regions at C3 and C4 (International 10-20 system of electrode placement)(Appendix I). The stimulation will be delivered with a train of 4-7 square wave pulses (75 μ s duration) while maintaining the inter-stimulus interval (ISI) at 2 msec. Stimulation intensity will be started at 150 Volts and increased by 20 Volts increments until robust response is obtained from several muscles. ⁽²²⁾

The tcMEPs will be recorded by a pairs of needles inserted in target muscles. Target muscles in the upper extremity will be deltoid (axillary nerve, C5-C6), biceps (musculocutanouse nerve, C5-C6), triceps (radial nerve, C7), abductor pollicis brevis (APB) (C8-T1) and trapeziuses (C4) when needed if

the level is above C4. In the lower extremity, tibialis anterior (TA), abductor hallucis (AH) and extensor digitorum brevis (EDB).⁽²²⁾

Somatosensory evoked potential monitoring

SSEPs will be elicited by the stimulation of the posterior tibial nerve at the ankle and median nerve at the wrist region. The cortical potentials of SSEP will be recorded from CP3 (2 cm behind C3) and CP4 (2 cm behind C4) in the upper extremities and CPz (2 cm behind CZ)/Fz in the lower extremities (depending on the 10–20 international electrode system).⁽²³⁾

The stimulation will be delivered by alternating stimulation of the posterior tibial nerve or the median nerve sites using biphasic 200 μ sec square wave pulses at a rate of 2.66/sec and intensity of 12-16 mA at median nerve & 40-60 mA at posterior tibial nerve. Each average consists of about 200 trials and with a band pass of 30–1000 Hz.⁽²³⁾

Spontaneous Electromyography

free running EMG will be monitored from all the recording muscles of the upper and lower limbs involved in the surgical level.

Baseline readings will be obtained before skin incision. SSEP will be analyzed for latency and peak-to-peak amplitude and MEP will be analyzed for amplitude and threshold. Stimulation will be alternated between SSEP and MEP in continuous order while free running EMG will be performed throughout surgery. The surgical team will be immediately informed of any significant IONM changes.⁽²⁴⁾

EMG Monitoring of Cranial Nerves

One pair of needle electrodes 1.5 cm apart from each other will be inserted to orbicularis oris and one pair to orbicularis oculi muscles for monitoring facial nerve functions. Another pair of needle electrodes will be inserted to masseter muscle for trigeminal nerve monitoring. For hypoglossal nerve monitoring , needle electrodes will be inserted to lateral site of tongue. For both glossopharyngeal and vagus nerves monitoring also needle electrodes will be placed to posterior wall of pharynx. Impedances of all electrodes should be below 2 kO. Direct electrical stimulation of nerves will be performed using bipolar hand probe to localize and find the trace of the nerve. Both free run EMG and triggered EMG of cranial nerves will be used.⁽²⁵⁾

Post operative evaluation :

- Full clinical neurological examination to asses any superadded neurological deficit

ETHICS OF RESEARCH

Research on human or human products:

- Prospective study: Informed consent will be taken from patients. In case of incompetent patients the informed consent will be taken from the guardians.
- Retrospective study: Confidentiality of records will be considered
- DNA / genomic material: Informed consent for DNA / genomic test and for research will be taken from patients. No further tests will be carried out except with further approval of committee and patients. If the samples will travel outside Egypt the researcher will be responsible for transportation and security approval.
- All drugs used in the research are approved by the Egyptian Ministry of Health

Research on animal:

- The animal species are appropriate for the test.
- After test, if the animal will suffer, it will be euthanized and properly disposed.
- After operation, it will have a proper postoperative care.

RESULTS

The results will be tabulated and analyzed according to the different findings.

DISCUSSION

Findings will be discussed in view of achievement of the aim of the study and will be compared with similar studies in literature.

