### 3 - Sensitivity

Positivity in diseased patients, expressed as percent =  $\frac{TP}{TP + FN} \times 100$

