### 4 - Specificity

Negativity in non-diseased subjects, expressed as percent =  $\frac{TN}{FP + TN} \times 100$

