### 5 - Positive Predictive value (PPV)

Percent of subjects with positive results who are diseased =  $\frac{TP}{TP + FP} \times 100$

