### 6 - Negative Predictive value (NPV)

Percent of subjects with negative test results who are non-diseased

$$= \frac{TN}{TN + FN} \times 100$$

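### Must the SAP require an alarm and a new deficit to share a territory before the patient counts as a true positive?

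*Protocol*

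**What the plan says.** The SAP defines sensitivity as "Positivity in diseased patients, expressed as percent", specificity as "Negativity in non-diseased subjects, expressed as percent", PPV as "Percent of subjects with positive results who are diseased" and NPV as "Percent of subjects with negative test results who are non-diseased". These are the standard formulas with the patient as the unit. Which monitoring change is positive, and what counts as diseased, is left open.

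The protocol supplies candidates but not definitions:

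- **Alarm.** The introduction mentions a 50% amplitude fall or 10% latency rise for SSEP, and an amplitude fall of more than 50% for MEP. Under Spontaneous Electromyography, the surgical team is told of significant changes, with no threshold. Monitoring Technique provides a recorded baseline for comparison.
- **Outcome.** Post operative evaluation calls for a "Full clinical neurological examination to asses any superadded neurological deficit". It gives no time point and no restriction to the monitored pathways.
- **Combination.** The introduction argues that "To use only a single modality is not enough for a successful and efficient neuromonitoring in neurosurgery". The SAP does not say whether the four measures are per modality, for any alarm, or both.

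**The concern.** The trial pools brain and spine lesions. SSEP and MEP are planned for both spinal and cranial operations, and cranial-nerve EMG is added when the brainstem is involved. The examination covers every function, while each modality covers one pathway. Two errors are possible on a literal reading:

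- An alarm in one territory and a deficit in an unrelated one are scored as a true positive. This inflates PPV and, for a combined alarm, sensitivity.
- In a per-modality table, a deficit that the modality could not detect is scored as its miss. This lowers sensitivity.

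The introduction also concedes that "SSEPs signal changes, however, are not always related to a postoperative neurological deficit", so unrelated alarms look foreseeable. The accuracy measures bear directly on the first aim, the usefulness of monitoring. With few deficits among 25 patients, one reclassified patient moves the result a long way.

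**Working it through.** The documents give no expected accuracy, deficit rate or sample-size derivation, so there is no planned figure to reproduce.

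**1. Is a wrong rule stated?** No. Items 3-6 fit either reading: diseased can mean any new deficit, or a new deficit in the monitored pathway. The mismatched true positive arises under one permitted reading only.

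**2. Does the introduction show that mismatches occur?** No. The sentence on SSEP changes is followed at once by a reported specificity of 27%. It concerns alarms in patients without a deficit, and items 4 and 5 already count those as false positives. The complement, 100% - 27% = 73%, is a false-alarm rate in patients without a deficit. It is not a rate of wrong-territory alarms in patients with one.

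**3. How large could the effect be for one modality?** From the protocol: N = 25. Assumed: D deficits, k of them in the modality's pathway, matched sensitivity s, and an unrelated-alarm rate f that is equal in all patients.

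- Unmatched TP = k[s + (1-s)f] + (D-k)f
- Matched TP = ks
- Alarms = unmatched TP + (N-D)f
- PPV = TP / alarms

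Take D = 4, k = 2, s = 0.99, f = 0.10:

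- Unmatched TP = 2(0.99 + 0.001) + 2(0.10) = 2.182
- Matched TP = 1.98
- Alarms = 2.182 + 21(0.10) = 4.282
- PPV = 2.182/4.282 = 51.0% unmatched, against 1.98/4.282 = 46.2% matched

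Other settings with D = 4 and f = 0.10:

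| k of 4 in pathway | s = 0.99: unmatched v matched PPV | s = 0.80: unmatched v matched PPV |
|---|---|---|
| 1 | 38.1% v 29.2% | 34.8% v 24.8% |
| 2 | 51.0% v 46.2% | 46.7% v 40.6% |
| 3 | 59.4% v 57.4% | 54.9% v 51.5% |
| 4 | gap 0.1 point | gap 1.5 points |

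If f is pushed to 0.73, the gap at k = 4 is still only 0.2 points (s = 0.99) or 3.1 points (s = 0.80). At k = 2 it is 18.4% v 10.5% (s = 0.99), but step 2 shows that 0.73 is not a documented value for f. The result turns on k and f, and the documents give neither.

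**4. What of sensitivity for one modality?** With k = 2, s = 0.99, f = 0.10, unmatched sensitivity is 2.182/4 = 54.5%, against 1.98/2 = 99% matched. The denominators differ: all deficits, or only those in the pathway. These are two different quantities, so the gap does not measure error in either.

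**5. What of a combined alarm?** Assume 4 deficits in monitored pathways, 6 alarms of which 4 are in deficit patients, and 19 true negatives (4 + 2 + 19 = 25). If one alarm in a deficit patient was in the wrong territory, then:

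- sensitivity goes from 4/4 (exact 95% CI 39.8-100%) to 3/4 (19.4-99.4%);
- PPV goes from 4/6 (22.3-95.7%) to 3/6 (11.8-88.2%).

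The intervals overlap almost wholly. The mismatch itself is posited.

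**The case for a change.** The strongest case for a change is that an unwritten rule invites case-by-case decisions once results are known. At 4 deficits, each such decision is worth 1/4 = 25 points of sensitivity. Coincidence is not far-fetched either: if unrelated alarms occur independently in 10% of patients, the chance of at least one among 4 deficit patients is 1 - 0.9^4 = 34.4%. Adopting the introduction's alarm thresholds would not produce a territory match.

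The textual point stands in full: the terms are undefined and no match is required. The 34.4% overstates the harm for a combined alarm. An extra unrelated alarm changes nothing in a patient who also alarmed in the right territory; it matters only where the right channel was silent.

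A matching rule also brings problems of its own. Glossopharyngeal and vagus nerves share one pharyngeal recording site, and deltoid and biceps are both C5-C6, so a strict match could reject true detections. A patient with two deficits, one signalled and one missed, needs a further convention. A wrong-territory alarm is both a missed deficit and an unconfirmed alarm, which a 2x2 table cannot hold. Because the SAP is written in the past tense, any rule added now may follow sight of the data. Matching alone would still leave the alarm threshold and the time of the examination unset.

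**Conclusion.** The omission is real, but it is a gap in detail that analysts can fill sensibly, and it does not call for a change to the plan. The formulas are correct and no stated rule credits an unrelated alarm. It is a judgement, not something the documents state, that specialists who place electrodes for the structures at risk would read alarm and deficit together. Accuracy per patient for any new deficit is in any case a legitimate measure of usefulness.

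The size cannot be established from the documents. At an assumed 10% unrelated-alarm rate with 4 deficits, the PPV gap runs from about 0.1 point (all deficits in pathway, 99% matched sensitivity) to about 10 points (one of four in pathway, 80%). For a combined alarm, one posited mismatch shifts estimates whose intervals already span 60 points or more. Strict matching would exchange one unstated convention for several contestable ones, with no clear gain in what 25 patients can show.

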**NCT number: not available**

**Document Date : 18 November 2021**

## Statistical analysis of the data

Data were fed to the computer and analyzed using the IBM SPSS software package version 20.0. (Armonk, NY: IBM Corp) Qualitative data were described using number and percent. **The Shapiro-Wilk test** was used to verify the normality of the distribution, and quantitative data were described using range (minimum and maximum), mean, standard deviation, median, and interquartile range (IQR). The significance of the results was determined at the 5% level.

### 1 - Chi-square test

For categorical variables, we compared different groups.

### 2 - Fisher's Exact or Monte Carlo correction

Correction for chi-square when more than 20% of the cells have expected count less than 5

### 3 - Sensitivity

Positivity in diseased patients, expressed as percent =  $\frac{TP}{TP + FN} \times 100$

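### SAP sections 3 to 6 plan sensitivity, specificity, PPV and NPV as bare percentages, with no confidence interval, although each is a proportion from a subset of 25 patients

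*SAP*

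**What the plan says.** SAP sections 3 to 6 are the only place where the accuracy of the monitoring is quantified. Section 3 gives sensitivity as "Positivity in diseased patients, expressed as percent", computed as TP/(TP + FN) × 100. Section 4 gives specificity as "Negativity in non-diseased subjects, expressed as percent", computed as TN/(FP + TN) × 100. Sections 5 and 6 define PPV and NPV in the same form. None of the four sections goes beyond the percentage.

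The SAP's general paragraph adds two statements that bear on the point: "Qualitative data were described using number and percent" and "The significance of the results was determined at the 5% level". The only inferential tools listed are the chi-square test and its Fisher or Monte Carlo alternative, and both compare groups.

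On size, the protocol (Subjects) says "Twenty five patients with different brain or spine lesions will be admitted to Neurosurgery Department". It gives no derivation of that number and no expected rate of deficits or alerts. The first aim is "To assess the usefulness of applying appropriate different neuromonitoring modalities in various neurosurgical operations with high risks of neural injury". The Discussion section says "Findings will be discussed in view of achievement of the aim of the study and will be compared with similar studies in literature".

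**The concern.** A percentage from a handful of patients carries little information unless its uncertainty is shown with it. The four measures have different denominators, and all of them come out of the same 25 patients. Two results that look identical as percentages can therefore rest on very different amounts of evidence.

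These are the SAP's only accuracy measures, and the first aim is to judge how useful the monitoring is. If accuracy is among the findings compared with the literature, the plan would set one point percentage against another. The protocol's own introduction cites SSEP accuracy that way (sensitivity 99%, specificity 27%). No estimate is biased by the omission. What is at stake is how firmly a reader may take the accuracy result.

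**Working it through.** **Is there a figure to reproduce?** No. The 25 is stated without inputs, and no precision target is given. The check is therefore what the planned percentages would hide at this sample size.

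**Inputs from the documents**
- Total: 25 patients (Protocol, Subjects).
- Formulas: SAP sections 3 to 6, which count patients or subjects.
- Meaning of *diseased*: the SAP does not define it. I take it as a new postoperative deficit, inferred from the protocol's Post operative evaluation, "Full clinical neurological examination to asses any superadded neurological deficit".

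**Assumptions, not in the documents**
- 3, 5 or 10 of the 25 patients have a new deficit, and all are detected.
- There are 2 false alerts. As an alternative, false alerts follow the 27% SSEP specificity cited in the protocol's introduction. With 3 deficits, 27% of the other 22 is 5.94, so about 6 true negatives and 16 false alerts.

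**Method.** The exact (Clopper-Pearson) two-sided 95% interval for x of n runs from the 2.5% quantile of Beta(x, n − x + 1) to the 97.5% quantile of Beta(x + 1, n − x). When x = n, the lower limit is 0.025^(1/n) and the upper limit is 100%.

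**All-detected sensitivity**
- 3/3: 0.025^(1/3) = 29.2%
- 5/5: 0.025^(1/5) = 47.8%
- 10/10: 0.025^(1/10) = 69.2%
- Limiting case, all 25 patients in one denominator: 0.025^(1/25) = 86.3%

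For comparison, 20/20 gives 0.025^(1/20) = 83.2%.

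**All four measures, exact 95% intervals**

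| TP, FN, FP, TN | Sensitivity | Specificity | PPV | NPV |
|---|---|---|---|---|
| 3, 0, 2, 20 | 3/3: 29.2–100% | 20/22: 70.8–98.9% | 3/5: 14.7–94.7% | 20/20: 83.2–100% |
| 5, 0, 2, 18 | 5/5: 47.8–100% | 18/20: 68.3–98.8% | 5/7: 29.0–96.3% | 18/18: 81.5–100% |
| 10, 0, 2, 13 | 10/10: 69.2–100% | 13/15: 59.5–98.3% | 10/12: 51.6–97.9% | 13/13: 75.3–100% |
| 3, 0, 16, 6 | 3/3: 29.2–100% | 6/22: 10.7–50.2% | 3/19: 3.4–39.6% | 6/6: 54.1–100% |

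**Does one measure always come off worst?** No.
- Third row: specificity spans 98.3 − 59.5 = 38.8 points and sensitivity 100 − 69.2 = 30.8, although specificity has the larger denominator.
- Fourth row: NPV spans 100 − 54.1 = 45.9 points and PPV 39.6 − 3.4 = 36.2. With few false alerts (first row) the order of these two is reversed.

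**Does the choice of method matter?** Yes. When x = n, the Wilson lower limit is n/(n + z²). With z² = 3.84146, 3/3 gives 3/6.84146 = 43.9%, against 29.2% exact.

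**The case against.** Four arguments can be made for leaving the plan as it is.

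*The general paragraph already covers this.* The 5% level is tied to significance, and no test or interval is attached to the accuracy measures. The rule of number and percent may well lead to counts being shown, and from a full two-by-two table a reader could work out the intervals. That much stands. But the rule is not linked to sections 3 to 6, and a count is not an interval.

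*No decision depends on a lower limit.* This is true: the documents set no accuracy target or hypothesis, and they do not define usefulness as accuracy. It limits the weight of the point. It does not remove it, because accuracy will still be reported and interpreted.

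*The definitions come first.* *Diseased* and *positive* are undefined in the SAP, and an interval cannot repair that. This is correct, and it is a separate matter. The interval is needed whatever definition is chosen.

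*The illustrations are invented.* The splits are assumptions and are labelled as such. The limiting case of 25/25 needs no split, and its lower limit is still only 86.3%.

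A reader might go further and infer that sensitivity and PPV must be the least precise of the four. The documents do not support this. It would require both deficits and alerts to be few, and no rate is given for either. The introduction describes multimodal specificity as high but gives no number, and the one specificity figure it does give (27%, for SSEP) points to many alerts.

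**Conclusion.** The point holds for all four measures: percentages are planned, no interval is planned in either document, and each denominator is part of a 25-patient cohort. On the assumed splits, a reported sensitivity of 100% would be compatible at the 95% level with a true value as low as 29.2% (3/3), 47.8% (5/5) or 69.2% (10/10).

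The absence of an interval follows from the text alone and needs no assumption. The sizes rest on the assumed numbers of deficits and alerts, and on reading *diseased* as a new postoperative deficit. No ranking of the four measures is claimed. Nor does the point show that 25 patients is the wrong number, since the documents state no precision target against which to judge it. This is a gap in reporting and interpretation that is cheap to close.

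**What to change.** In SAP sections 3 to 6:
- Report each measure as n/N with a two-sided 95% confidence interval.
- Name one method in advance. Exact Clopper-Pearson is one option and Wilson is also acceptable, but the choice should be fixed before the accuracy results are seen, because the two differ materially at these sizes.
- State that conclusions about accuracy, and any comparison of accuracy with the literature, rest on the interval and not on the percentage alone.
- If accuracy is also reported by modality, give the same interval there.
- Report a measure with a zero denominator as not estimable.

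The cost is a few lines of SAP text and a few minutes of computation. No extra patients or data are needed, because the existing two-by-two counts are enough. The downside is that the reported accuracy will look less certain.
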